7.4 Plinabulin

Dose delay and/or dose reduction of plinabulin should be considered for significant tumor pain, hypertension, or constipation (including ileus). As a single agent, plinabulin has not been associated with severe hematological toxicity. If a patient experiences a Grade 3 or 4 non-hematologic AE related to plinabulin or the combination of plinabulin with nivolumab, OR requires more than a 14-day delay of scheduled treatment due to toxicity related to plinabulin, regardless of severity, the dose of plinabulin will be reduced per Table 2.

If the same toxicity with same or higher severity recurs despite dose reduction, plinabulin will be discontinued and the patient will continue receiving nivolumab alone. Only one dose reduction for plinabulin is permitted. See [Table 2](#) Dose Modification for Plinabulin.

Treatment with plinabulin will be discontinued permanently for a concomitant elevation of aspartate aminotransferase (AST) or alanine aminotransferase (ALT) levels of more than 3 times the institutional upper limit of normal and bilirubin levels of more than 2 times the institutional upper limit of normal.

Table 2. Dose Modification for Plinabulin.

Condition	Action
First Occurrence of grade 3 or 4 non-hematologic AE assessed as possibly, probably or definitely related to plinabulin	Reduce plinabulin by 10 mg/m ² on subsequent administrations
Second occurrence of Grade 3 or 4 non-hematologic AE assessed as as possibly, probably or definitely related to plinabulin	Discontinue plinabulin (patients may continue on nivolumab alone)
AST and/or ALT > 3 x ULN AND total bilirubin > 2 x ULN assessed as as possibly, probably or definitely related to plinabulin	Discontinue plinabulin (patients may continue on nivolumab alone)

8.0 SAFETY PARAMETERS AND DEFINITIONS:

8.1 Adverse Events:

Adverse events will be collected after the patient has taken the first dose of study drug. After discontinuation from treatment, patients must be followed for all existing AEs for 28 calendar days after the last dose of study drug or until another anti-cancer therapy is initiated.

Clinical Study Protocol 9602
Drug Substance: plinabulin
IND: 129799
Protocol v5.1
Date 7/15/2017

Prior to beginning study treatment, study site personnel will note the occurrence and nature of each patient's medical condition(s). During the study, site personnel will again note any change in the condition(s) and/or the occurrence and nature of any adverse events. Toxicities are to be graded according to the NCI CTC version 4.0.

A description of the event, including its date of onset and resolution, any action taken should be provided along with the investigator's assessment of causality. An event that is due to unequivocal progression of disease should not be reported as an AE. Any adverse events leading to a treatment interruption or dose reduction along with all grades 2 and higher adverse events related to study medication must be recorded on a case report form (CRF).

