7.1 Definition of Dose-Limiting Toxicities (DLT)

A DLT is defined as one of the following adverse events reported during the DLT observation period, if considered to be definitely, probably, or possibly related to either study regimen by the investigator; and fulfills any one of the following criterion using NCI CTCAE Version 4.0:

1. Nonhematologic toxicity as follows:

- a) Grade 4 nonlaboratory toxicity
- b) Grade 3 nonlaboratory toxicity (for example, nausea, vomiting, and diarrhea) lasting >3 days despite optimal supportive care.
- c) Any Grade 3 or Grade 4 laboratory value if:
 - i) Medical intervention is required to treat the patient, or ii)
The abnormality persists for >1 week.

Note: Liver function abnormality: For patients with liver metastasis who begin treatment with Grade 2 aspartate aminotransferase (AST) or alanine amino transferase (ALT), if AST or ALT increases by greater than or equal to 50% relative to baseline and lasts for at least 7 days

2. Hematologic toxicity, as follows:

- a) Grade 4 thrombocytopenia and Grade 4 anemia.
- b) Other grade 4 toxicities lasting ≥ 7 days, or
- c) Grade 3 thrombocytopenia if associated with bleeding and requires platelet transfusion, or
- d) Febrile neutropenia Grade 3 or Grade 4

3. Any grade 5 toxicity

4. Any other significant toxicity deemed by the primary investigator and the sponsor to be dose limiting, for example:

- a) Any toxicity that is possibly related to study treatment that requires the withdrawal of the patient from the study
- b) A delay of > 14 days due to persistent Grade ≥ 2 toxicities in initiating the subsequent cycle, with the exception of Grade 2 fatigue

Any infusion or hypersensitivity reactions occurring during the infusion of the drug are not considered dose-related and therefore will NOT be considered to be a DLT.

Attribution of adverse events.

Unrelated: This relationship suggests that there is no association between the study drug and the reported event.

Unlikely: This relationship suggests that the association between the study drug and the reported event is unlikely.

Possible: This relationship suggests that treatment with the study drug caused or contributed to the AE, ie, the event follows a reasonable temporal

sequence from the time of drug administration or follows a known response pattern to the study drug, but could also have been produced by other factors.

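### Table 2 row 1 orders a second plinabulin cut at the first Grade 3 or 4 event in a patient already reduced for a milder toxicity, although section 7.4 allows only one reduction.

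*Combined protocol and SAP*

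**What the plan says.** All the dose rules at issue are in section 7.4 of the protocol and its Table 2.

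The text gives three routes to a plinabulin reduction. Two are mandatory: a related Grade 3 or 4 non-hematologic event, or a treatment hold that exceeds the length named here: "14-day delay of scheduled treatment due to toxicity related to plinabulin, regardless of severity, the dose of plinabulin will be reduced per Table 2". The third is discretionary and carries no grade threshold: it names significant tumor pain, hypertension and constipation as reasons to consider a delay or reduction.

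Two limits follow. The recurrence rule is "If the same toxicity with same or higher severity recurs despite dose reduction, plinabulin will be discontinued", with nivolumab continuing alone. The cap is "Only one dose reduction for plinabulin is permitted". The next sentence refers the reader to Table 2.

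Table 2 has three rows.

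- Row 1: "First Occurrence of grade 3 or 4 non-hematologic AE assessed as possibly, probably or definitely related to plinabulin", with the action "Reduce plinabulin by 10 mg/m"².
- Row 2: "Second occurrence of Grade 3 or 4 non-hematologic AE assessed as" related to plinabulin, with the action to discontinue it.
- Row 3: a combined transaminase and bilirubin elevation, with the action to discontinue.

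No row mentions a delay, an earlier reduction or the cap.

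**The concern.** Row 1 counts Grade 3 or 4 events. The cap counts reductions. The two counts agree only when every first reduction follows a Grade 3 or 4 event, and section 7.4 does not require that. A patient can use up the one permitted reduction on a milder toxicity and then have a first Grade 3 or 4 event. Row 1 then orders another cut.

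What is at stake is the dose of the investigational drug after severe toxicity. A site that works from the table alone would re-treat a patient whom the text takes off plinabulin, or would exceed the protocol's own limit on reductions.

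**Working it through.** The plan gives no figure to reproduce here, so the check applies the text and the table separately to one path. The events are taken to be non-hematologic and judged related to plinabulin, so that both sets of rules apply.

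**Step 1, first reduction below Grade 3.** Suppose a Grade 2 plinabulin toxicity delays treatment by more than 14 days. The text requires a reduction under Table 2. No row matches. The only step in the table is 10 mg/m², so take that as the size (an assumption). From the 30 mg/m² dose (section 5.0, Dose rationale): 30 − 10 = 20 mg/m². The permitted reduction is now used.

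**Step 2, first Grade 3 or 4 event.**

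| Rule | Same toxicity returns | Different toxicity |
|---|---|---|
| 7.4 recurrence rule | Discontinue (severity is higher) | Does not apply |
| 7.4 Grade 3 or 4 trigger | Reduce under Table 2 | Reduce under Table 2 |
| 7.4 cap | No second reduction | No second reduction |
| Table 2 row 1 | Cut by 10 mg/m² | Cut by 10 mg/m² |
| Table 2 row 2 | Not met: first such event | Not met: first such event |

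Under row 1 the dose would be 20 − 10 = 10 mg/m². For a patient who started at 20 mg/m², the first dose-escalation level in section 5.1.3, the same path gives 20 − 10 = 10 and then 10 − 10 = 0 mg/m².

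**Same toxicity.** The specific recurrence rule and the cap both exclude another cut, and the recurrence rule supplies the action: stop. Row 1 is the part that is wrong.

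**Different toxicity.** The trigger in the text and row 1 both order a cut. The cap forbids it. Neither the recurrence rule nor row 2 is met, and row 3 helps only if the event is the liver pattern it describes. Section 7.0 says what must resolve before treatment resumes, but not the plinabulin dose on resuming. No stated action is left.

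**When the first reduction followed a related Grade 3 or 4 non-hematologic event**, a second such event meets row 2, which stops plinabulin. The problem is therefore confined to first reductions made for something milder.

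**Delay row.** Of the two mandatory triggers, the table has a row for the Grade 3 or 4 event and none for the delay.

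**The case against.** The strongest reply is that the cap is unconditional and stands immediately before the reference to Table 2. Read in order, the section does not let row 1 produce a second cut, and the table merely omits a rule stated above it. For recurrence of the same toxicity this stands as to intent. A reader might infer that text and table leave that case undecided, but the documents do not support that: the recurrence rule and the cap both point to stopping. What remains is that row 1, applied literally, says otherwise. For a different toxicity the reply fails, because the cap removes the ordered action and puts nothing in its place. The investigator may withdraw a patient for safety, but that is a general discretion, not a plinabulin dose rule.

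Two other stronger readings are tempting.

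- One is that the size of the delay-triggered reduction is unknown. The text points to a table with a single step of 10 mg/m², and the planned doses of 20 and 30 mg/m² are one such step apart. The missing row is a gap in the table; the intended size is hardly in doubt.
- The other is that the plan expects long delays from Grade 2 toxicity, because section 7.1 lists "A delay of > 14 days due to persistent Grade ≥ 2 toxicities in initiating the subsequent cycle". That item is an example of what may be deemed dose limiting, and it is not specific to plinabulin. Section 7.0 asks only that related Grade 3 or 4 toxicities resolve before treatment restarts, and it accepts tolerable Grade 2. The path is reachable, but nothing shows how often it would be taken.

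**Conclusion.** Row 1 is wrong as written for a patient whose plinabulin was already reduced for a toxicity below Grade 3. It contradicts the recurrence rule and the cap when the same toxicity returns at Grade 3 or 4. When the severe toxicity is a different one, it orders a cut that the cap forbids, and the protocol has no alternative. The absent delay row is a minor companion point.

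This rests on two assumptions: that a discretionary reduction counts toward the cap, which the cap's wording supports because it makes no exception, and that the event is related to plinabulin and non-hematologic. The 10 mg/m² size assumed for the first cut affects only the illustrative doses.

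The issue is an internal inconsistency in a safety rule, on a narrow path. The number of patients affected, out of the 39 planned in section 9.1, cannot be derived. A reader might infer some effect on the trial's operating characteristics, but there is none: the two-stage design, its error rates and the response-rate analysis do not depend on this rule.

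**What to change.** Change Table 2 as follows.

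- **Row 1:** limit it to patients with no prior plinabulin reduction.
- **Row 2:** discontinue plinabulin at a second related Grade 3 or 4 non-hematologic event, at any such event after any prior plinabulin reduction, and when the same toxicity returns at equal or greater severity after a reduction. The last clause also brings into the table recurrences below Grade 3, which the text already stops.
- **New row:** for a delay of more than 14 days caused by plinabulin toxicity of any grade, make the single 10 mg/m² reduction.

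Row 3 and the 7.4 text can stay as they are. The text's instruction to follow Table 2 would then lead to a stop wherever the cap now blocks row 1.

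The cost is two edited rows and one added row, with no change to sample size or analysis. There is one small clinical downside. A few patients with a new and different Grade 3 or 4 toxicity after a reduction would stop plinabulin and continue on nivolumab alone. That is the conservative choice, and the investigator and sponsor should confirm it.

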Probable: This relationship suggests that a reasonable temporal sequence of the event with drug administration exists and, based upon the known pharmacological action of the drug, known or previously reported adverse reactions to the drug or class of drugs, or judgment based on the investigator's clinical experience, the association of the event with the study drug seems likely. The event disappears or decreases on cessation or reduction of the dose of study drug.

Definite: This relationship suggests that a definite causal relationship exists between drug administration and the AE, and other conditions (concurrent illness, progression/expression of disease state, or concurrent medication reaction) do not appear to explain the event.

Nivolumab

There will be no dose reductions for nivolumab, dose delays will be discussed below. If an immune related adverse event (irAE) is suspected, a thorough evaluation should be conducted in an effort to rule out neoplastic, infectious, metabolic, toxin or other etiologic causes prior to diagnosing an irAE. Serological, immunological, and histological (biopsy) data should be considered to support the diagnosis of an immune-related toxicity. Systemic corticosteroids (1-2mg/kg/day) are indicated for all grade 3 or grade 4 irAEs if not otherwise specified as below. Steroid should be tapered once symptoms improve to Grade 1 or less and tapered over at least 1 month. Nivolumab should be permanently discontinued for

- Life-threatening or non-hematologic grade 4 toxicity
- Any severe or Grade 3 treatment-related adverse reaction that recurs.
- Inability to reduce corticosteroid dose to ≤ 10 mg of prednisone or equivalent/day within 12 weeks
- Persistent Grade 2 or 3 treatment-related adverse reactions that do not recover to Grade 1 or resolve within 12 weeks after last dose of nivolumab.

Table 1: Dose modification guidelines for toxicities related to Nivolumab

Adverse reaction	Severity	Dose modification*
Pneumonitis	Grade 2	Withhold dose
	Grade 3 or 4	Permanently discontinue
Hepatitis	Aspartate aminotransferase (AST)/or alanine aminotransferase (ALT)	Withhold dose

Clinical Study Protocol 9602
Drug Substance: plinabulin
IND: 129799
Protocol v5.1
Date 7/15/2017

	more than 3 and up to 5 times the upper limit of normal or total bilirubin more than 1.5 and up to 3 times the upper limit of normal	

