	AST or ALT more than 5 times the upper limit of normal or total bilirubin more than 3 times the upper limit of normal	Permanently discontinue
Hypophysitis Adrenal Insufficiency Hyperglycemia Rash Colitis or Diarrhea	Grade 2 or 3	Withhold dose
	Grade 4	Permanently discontinue
Nephritis and renal dysfunction	Serum creatinine more than 1.5 and up to 6 times the upper limit of normal	Withhold dose
	Serum creatinine more than 6 times the upper limit of normal	Permanently discontinue
Encephalitis	New-onset moderate or severe neurologic signs or symptoms	Withhold dose
	Immune-mediated encephalitis	Permanently discontinue
Other	Grade 3 first occurrence	Withhold dose
	Recurrence of same grade 3 AE	Permanently discontinue
	Grade 4	Permanently discontinue
* if treatment is withheld, it should be resumed once the adverse events return to grade 0 or 1. If this does not happen in >12 weeks then treatment should be discontinued and the patient should be taken off study		

Patients should receive appropriate supportive care measures as deemed necessary by the treating investigator. Please refer to “Immune mediated adverse reaction management guide” published by Bristol-Myers Squibb for additional recommendations regarding irAE management.

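### One sentence in Section 7.4 keeps nivolumab going after a recurrent combination-related toxicity for which the nivolumab rules require a permanent stop

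*Combined protocol and SAP*

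**What the plan says.** **Section 7.4 (Plinabulin).** The rule applies to a "Grade 3 or 4 non-hematologic AE related to plinabulin or the combination of plinabulin with nivolumab", and also to any plinabulin-related toxicity, whatever its grade, that delays treatment by more than 14 days. At the first event plinabulin is reduced according to Table 2. For a later event of the "same or higher severity recurs despite dose reduction, plinabulin will be discontinued and the patient will continue receiving nivolumab alone". The paragraph then refers the reader to Table 2.

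**Table 2.** At a second Grade 3 or 4 non-hematologic event with at least a possible relation to plinabulin, plinabulin stops and the patient *may* stay on nivolumab alone.

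**Nivolumab subsection of Section 7.** The permanent-discontinuation list includes "Any severe or Grade 3 treatment-related adverse reaction that recurs" and "Life-threatening or non-hematologic grade 4 toxicity".

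**Table 1 (nivolumab).** The 'Other' row withholds the dose at "Grade 3 first occurrence" and permanently discontinues it at "Recurrence of same grade 3 AE" or at Grade 4. The grouped row "Hypophysitis Adrenal Insufficiency Hyperglycemia Rash Colitis or Diarrhea" withholds at Grade 2 or 3 and permanently discontinues at Grade 4. The footnote adds: "if treatment is withheld, it should be resumed once the adverse events return to grade 0 or 1".

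**The concern.** An event attributed to the combination falls under both sets of rules. Section 7.4 names such events, and they are treatment-related for the purposes of the nivolumab list. When one recurs, 7.4 tells the investigator that nivolumab goes on, and the nivolumab rules say it stops for good. A physician who follows 7.4 literally gives nivolumab again after an event that the same protocol treats as a permanent stop. Two physicians could treat the same event in opposite ways and each cite the text.

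The scenario is plausible. The Background reports diarrhea in 34% of patients on plinabulin alone, 58% on plinabulin plus docetaxel, and 8% on nivolumab. These are not recurrence rates, and the 58% includes the effect of docetaxel. They show only that a toxicity could reasonably be attributed to both drugs.

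**Working it through.** The plan states no figure on this point, so the check sets the rules side by side for one scenario: a non-hematologic toxicity attributed to the combination.

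| Event | 7.4 text | Table 2 | Nivolumab list | Table 1, 'Other' row |
|---|---|---|---|---|
| First, Grade 3 | reduce plinabulin | reduce by 10 mg/m² | no stop | withhold nivolumab |
| Recurs at Grade 3 | stop plinabulin; nivolumab *will* continue | stop plinabulin; nivolumab *may* continue | stop nivolumab | stop nivolumab |
| Recurs at Grade 4 | stop plinabulin; nivolumab *will* continue | stop plinabulin; nivolumab *may* continue | stop nivolumab | stop nivolumab |

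**Step 1: which grade sequences are affected.** With both events at Grade 3 or 4 and the second at least as severe as the first, there are three sequences: 3 then 3, 3 then 4, and 4 then 4. In the last, the list has already stopped nivolumab at the first event. At that point 7.4 asks only for a plinabulin reduction, so both rules can be followed. The contradiction is live in the other two. This counts paths through the rules and says nothing about frequency.

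**Step 2: where Table 2 stands.** Section 7.4 sends combination events to Table 2. Under the attribution definitions in Section 7, a possible relation means that the drug caused or contributed to the event. A combination event is therefore at least possibly related to plinabulin and falls within Table 2. The *may* in that table is a permission, and a permission is compatible with the nivolumab stopping list. The *will* in 7.4 is not, so 7.4 disagrees both with the nivolumab rules and with the table it cites.

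**Step 3: whether any text decides between the rules.**
- Section 7.0 says to what grade toxicities should resolve before treatment restarts, and lets the most severe toxicity govern dose modification. That chooses between toxicities. It does not choose between opposite actions for one toxicity.
- The end-of-treatment section lists unacceptable toxicity without tying it to the nivolumab list. It also lets the investigator withdraw a patient for safety. Neither provision ranks the two rules.

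**Step 4: what lies outside the point.** Table 1 already stops nivolumab at a first Grade 3 pneumonitis. The hepatitis, nephritis and encephalitis rows are not set by CTC grade. For a toxicity attributed to plinabulin alone, any conflict depends on how widely treatment-related is read in the list, so such events are left out.

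**The case against.** The strongest reply is that the text can be read together. Section 7.4 is about plinabulin, and nivolumab has its own subsection, list and table. On that reading, continuing nivolumab alone means that stopping plinabulin does not end study treatment, while nivolumab stays under its own rules. Table 2 is already permissive, the investigator may withdraw a patient for safety at any time, and most clinicians would probably obey the stopping list. The path is also narrow. It needs attribution to the combination, a first Grade 3 event, recovery, a plinabulin reduction, resumed nivolumab, and then the same toxicity at Grade 3 or 4, in a single-center trial of 39 patients.

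Much of this stands. It makes the fault one of wording in a single sentence, and it rules out the inference that investigators are compelled to re-dose. It does not remove the contradiction: 7.4 gives a direct instruction on nivolumab, without exception, and nothing makes it subject to the nivolumab rules.

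Two stronger readings are tempting. A reader might infer that Table 2 is part of the contradiction or does not reach combination events. Step 2 shows that it does reach them and that its permission fits the list. A reader might also infer a second contradiction inside the nivolumab rules, because the Table 1 row with colitis or diarrhea has no stop for a recurrent Grade 3 event and the footnote says to resume. The list stands directly above that table and covers any recurrent Grade 3 treatment-related reaction, so it supplements the row.

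**Conclusion.** The point holds for a non-hematologic toxicity attributed to the combination that is first Grade 3 and recurs at Grade 3 or 4 after plinabulin reduction. There the *will* in 7.4 contradicts the nivolumab list and the Table 1 'Other' and Grade 4 entries, disagrees with the *may* in Table 2, and is not subordinated to any of them.

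This rests on the wording of the rules and on one reading: that a combination-attributed event counts as treatment-related, and as related to each drug. No number of patients can be given. The nearest figure in the documents is 7% Grade 3 or 4 treatment-related events on nivolumab in the phase III squamous trial, which is neither a recurrence rate nor a rate for this combination.

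A reader might infer that the conflict disturbs the trial's results. The documents do not support that. The analysis population in Section 9.2 and the response thresholds in Section 9.1 do not depend on which instruction is followed, and ORR, alpha, power and DLT counts are unaffected. What is at stake is patient safety and consistent dosing, and for that reason the sentence should be corrected.

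**What to change.** In Section 7.4, replace the end of the recurrence sentence with: *the patient may continue receiving nivolumab alone, unless the event is considered related to nivolumab or the combination and meets a nivolumab permanent-discontinuation criterion (list or Table 1).*

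The attribution condition matters. The Grade 4 item in the list has no attribution limit, and treatment-related can be read to include plinabulin. A bare reference to the list could therefore stop nivolumab for toxicities due to plinabulin alone, such as hypertension or ileus, where Table 2 allows it to continue. With the wording above, those patients may stay on nivolumab, and so may patients with low-grade events who enter 7.4 through the 14-day-delay route.

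A matching cross-reference in Table 2 and in the Table 1 resume footnote would be optional tidying.

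The cost is one clause in a protocol amendment, with no added visits, procedures or patients.

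### Section 7.4 says nivolumab will continue after a recurrent severe event in some cases where the nivolumab rules require a permanent stop

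*Combined protocol and SAP*

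**What the plan says.** Section 7.4 (Plinabulin) requires a plinabulin dose reduction after a "Grade 3 or 4 non-hematologic AE related to plinabulin or the combination of plinabulin with nivolumab", or after a toxicity-related delay of more than 14 days. Only one reduction is allowed. If the same toxicity comes back at equal or greater severity, "plinabulin will be discontinued and the patient will continue receiving nivolumab alone". The sentence carries no exception. The table it points to, Table 2, is worded differently for a second Grade 3 or 4 event: "Discontinue plinabulin (patients may continue on nivolumab alone".

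The nivolumab rules come earlier in section 7.0, under the Nivolumab heading. The list of reasons for permanent discontinuation includes "Life-threatening or non-hematologic grade 4 toxicity" and "Any severe or Grade 3 treatment-related adverse reaction that recurs". Table 1, for toxicities related to nivolumab, then gives actions by event:

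- **Pneumonitis:** permanent stop at Grade 3 or 4.
- **"Hypophysitis Adrenal Insufficiency Hyperglycemia Rash Colitis or Diarrhea":** withhold at Grade 2 or 3, permanent stop at Grade 4.
- **Other:** withhold at a first Grade 3 event; permanent stop at "Recurrence of same grade 3 AE" and at Grade 4.

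The footnote to Table 1 adds that "if treatment is withheld, it should be resumed once the adverse events return to grade 0 or 1".

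**The concern.** An event can be attributed to both drugs; section 7.4 provides for this by naming the combination. Such an event falls under the plinabulin rule and the nivolumab rule at once. On some recurrences the 7.4 text says nivolumab goes on, while the nivolumab section says it stops for good.

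What is at stake is patient safety. A physician who follows 7.4 as written would give nivolumab again to a patient who has met the protocol's own permanent-stop criterion for it. Section 7.0 requires recovery before treatment restarts, which governs the timing of re-challenge but does not forbid it. A cautious physician who stops nivolumab departs from a written instruction in 7.4.

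**Working it through.** The protocol states no figure on this point and no arithmetic applies. The check sets the two rules side by side for one kind of event: non-hematologic, attributed to both drugs, first seen at Grade 3 or 4, and recurring at the same or a higher grade after plinabulin reduction.

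**Is the sequence reachable?** Yes. For an event in the 'Other' category, a first Grade 3 occurrence leads to nivolumab being withheld and, after recovery to grade 0 or 1, resumed. Plinabulin is reduced by 10 mg/m² under Table 2. The patient is then on both drugs when the event recurs.

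**What does each rule then say about nivolumab?**

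| Table 1 category | Grades | 7.4 text | Nivolumab list | Table 1 | Result |
|---|---|---|---|---|---|
| Other | 3 then 4 | continue | stop | stop | conflict |
| Other | 3 then 3 | continue | stop | stop | conflict |
| Hypophysitis to diarrhea | 3 then 4 | continue | stop | stop | conflict |
| Hypophysitis to diarrhea | 3 then 3 | continue | stop | withhold, then resume | nivolumab rules disagree with each other |
| Pneumonitis | first event 3 or 4 | not reached | stopped at first event | stopped at first event | no conflict at recurrence |
| Other, or hypophysitis to diarrhea | first event 4 | not reached | stopped at first event | stopped at first event | no conflict at recurrence |

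For pneumonitis at first Grade 3, the early stop comes from Table 1 alone. The hepatitis, nephritis and encephalitis rows are defined by laboratory multiples or by signs, not by grade, and were not laid out this way. Reductions triggered only by a delay of more than 14 days were also left out.

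**Does any text settle precedence?** Three candidates were examined.

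1. Section 7.0 bases dose modification on the most severe toxicity. That ranks several toxicities against one another; it does not choose between two drugs' rules for a single toxicity.
2. The withdrawal procedures in section 6.0 end participation for unacceptable toxicity and let the investigator withdraw a patient for safety. Neither provision defines unacceptable toxicity or mentions the conflict.
3. The verbs do not help. Section 7.4 says 'will', while the nivolumab list is introduced with 'should', so on wording alone the less safe instruction is the firmer one.

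**Does Table 2 share the problem?** No. Its 'may' leaves room for the nivolumab rules to apply.

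**The case against.** The best defense is structural. Section 7.4 is about plinabulin, and it can be read as saying only that stopping plinabulin does not by itself end nivolumab, which remains under its own rules. Table 2, to which 7.4 sends the reader, is worded that way. The fact that nivolumab cannot 'continue' after an earlier stop, as with Grade 3 pneumonitis, may also seem to show that 7.4 presupposes nivolumab is still permitted. Finally, a recurrent Grade 3 or a Grade 4 event is an obvious candidate for unacceptable toxicity, which ends participation.

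Much of this stands. It is the sensible clinical reading and probably the intended one, and it lowers the practical risk. It does not remove the conflict. In the pneumonitis case nivolumab has gone before the recurrence, so 7.4 has nothing to continue. In the conflicting cases the patient is still eligible for nivolumab when the event recurs, and that one event triggers both rules. The presupposition has to be supplied by the reader, against a sentence without exceptions.

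The objection is also right about one category. A reader might infer that every recurrent Grade 3 event attributed to both drugs, diarrhea included, shows 7.4 contradicting the nivolumab rules as a whole. The documents do not support that. For the hypophysitis-to-diarrhea row, Table 1 withholds and then resumes, which is compatible with 7.4. The bullet on recurrent Grade 3 reactions is what disagrees, and it would disagree with Table 1 even if 7.4 were deleted. That is a separate inconsistency within the nivolumab section.

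**Conclusion.** The contradiction is real and narrow. It applies to non-hematologic events attributed to both drugs that go from Grade 3 to Grade 4 (pneumonitis excepted), and to those in the 'Other' category that go from Grade 3 to Grade 3. It sits in the word 'will' in the 7.4 text. It should be corrected because a stated rule, followed literally, gives the less safe instruction.

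The size cannot be expressed as a rate. The documents give no frequency for recurrent Grade 3 or 4 events attributed to both drugs; that the number is low is an expectation, not a figure from the protocol. A reader might infer a frequency from the Background section, which lists diarrhea at 58% with plinabulin plus docetaxel and 8% with nivolumab. Neither supports this: the first is regardless of causality, neither states a grade, and neither concerns recurrence.

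Two further inferences should be resisted. Events attributed to plinabulin alone are outside this point, since the list stands under the Nivolumab heading and Table 1 is limited to nivolumab-related toxicity. Nor does the primary analysis change: section 9.2 defines its population by treatment at the MTD and receipt of at least one dose, and the two-stage response boundaries do not depend on which drug is stopped later.

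The conclusion assumes that an event related to the combination can be related to nivolumab for the purposes of Table 1.

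**What to change.** Replace the sentence in 7.4 with wording such as: *Plinabulin is stopped. Nivolumab may be given alone unless one of its permanent-discontinuation criteria (nivolumab list or Table 1) is met; withholding and resumption of nivolumab follow Table 1.*

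The exception should name permanent-discontinuation criteria only. If temporary withholding criteria were included as a bar, the new sentence would itself clash with the Table 1 footnote on resuming treatment.

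Separately, the sponsor should decide whether a recurrent Grade 3 event in the hypophysitis-to-diarrhea row stops nivolumab or only withholds it, and align the list and Table 1.

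The cost is a wording amendment. Sample size, visits and analysis are unchanged.
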